Based on the findings of the qualitative interviews above, we will develop a questionnaire to elicit the preferences of men in surveillance for possible Exit Strategies. Without knowing the outcomes of the interviews, it is not possible at this stage to specify the method we will use. If it is possible to describe all the Exit Strategies in terms of a set of common attributes, then a discrete choice experiment (DCE) method will be used to elicit preferences. Each of the attributes will be assigned at least two levels (the levels will be decided from a combination of interview outcomes and expert opinion). Once levels have been assigned, a range of hypothetical Exit Strategies can be defined in terms of the attributes and levels (the final number of strategies is a function of the numbers of attributes and levels). The DCE will present men with a series of pairwise choices between two hypothetical strategies, and for each choice, they will be asked which they would prefer. The resulting choices will be analysed to reveal preferences for Exit Strategies and willingness to trade between them (Ryan 2007).

If it is not possible to define all the Exit Strategies in terms of a set of common attributes, then preferences will need to be elicited for each possible Exit Strategy individually. In this case, it is proposed to elicit preferences using the contingent valuation (CV) method. With this method, men will be presented with descriptions of the strategies and asked first to rank them from least preferred to most preferred. Maximum willingness to pay (WTP) for each strategy will then be elicited using a marginal approach (Shackley & Donaldson 2002). With this method, individuals are asked their WTP

for their least preferred programme and then subsequently asked how much more they would be prepared to pay for their next most preferred strategy.

As this questionnaire will be developed on the basis of the results from the earlier work packages, the precise content is not currently known and will require an amendment to ethics and HRA nearer the time.

Sample

The generation of the sample for the survey will be the same, irrespective of which method is used. The sample will be men in surveillance.

Identifying men

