We will ask two screening centres (Northeast & Cumbria and one other) centres to provide names, addresses of a random sample of men in surveillance to the research team using processes described in the previous survey section. The research team will send written information (covering letter, PIS, consent form, reply paid envelope) and then arrange for a telephone call to those who reply to administer the questionnaire.

Sample size

Based on previous experience with telephone surveys with vascular patients, where an approximate 60% response rate was achieved, we expect we will need to contact 500 men to achieve 300 responses (Michaels et al 2021). The sample size is based on precedence, where the literature shows that the majority of DCE sample sizes range between 100 and 300 (de Bekker-Grob 2015). Precedence is used because sample size calculations are difficult to estimate *a priori* without knowing the number of attributes and levels that will be included in the DCE. Based upon the CV literature and previous experience with the technique (Lin 2013, Shackley and Dixon 2014), a sample of 300 will be sufficient for meaningful analysis of WTP data.

Data collection

The telephone survey will be administered by the Research Associate with support from the Qualitative Researcher if necessary. Men will be asked to give verbal consent prior to the questionnaire being administered. We expect each telephone call to last no more than 20 minutes, based on our previous study where the average interview time was 13 minutes (Wickramasekera 2019).

Analysis

For the DCE, choice data will be modelled using a conditional logic model. Regression coefficients will be used to estimate the relative importance of attributes and the marginal rates of substitution will be calculated (i.e. trade off preferences for Exit Strategy characteristics) (de Bekker-Grob 2012). Latent class models will be used to analyse individual heterogeneity and to identify subsets of patients with

varying preferences (Hole 2016). For CV, the relative strength of men's preferences for the strategies will be estimated from calculating mean and median WTP values and testing for differences by using t-tests and Mann–Whitney U tests. Multivariate regression analyses will be performed to examine possible determinants of stated WTP and determine how WTP varies by different group characteristics. We will consider the use of a weighted sample here to address non-response bias.

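### If contingent valuation is used, the protocol names an independent-samples test (Mann–Whitney U) for comparing willingness to pay between strategies that the same men have all valued

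*Protocol*

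**What the plan says.** The text is in Protocol section 5, Work Package 2, part 2 (Survey to measure men's preferences).

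- **When it applies.** A discrete choice experiment is used if the strategies share a common set of attributes. Otherwise: "In this case, it is proposed to elicit preferences using the contingent valuation (CV) method".
- **What each man does.** Under that method "men will be presented with descriptions of the strategies and asked first to rank them from least preferred to most preferred".
- **How WTP is obtained.** "Maximum willingness to pay (WTP) for each strategy will then be elicited using a marginal approach". The man is asked his WTP "for their least preferred programme and then subsequently asked how much more they would be prepared to pay for their next most preferred strategy".
- **How it is analysed.** Under Analysis, the sentence opens with its purpose: "the relative strength of men's preferences for the strategies will be estimated from" the WTP data. The method it gives is "calculating mean and median WTP values and testing for differences by using t-tests and Mann–Whitney U tests". The next sentence uses regression to see how WTP varies with the men's characteristics.

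For the WTP data, the protocol names no paired test, signed-rank test, repeated-measures model or allowance for clustering within man.

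**The concern.** Each man supplies one WTP per strategy, and each later value is an earlier value from the same man plus an increment. The values being compared are therefore repeated measures on one sample of men, not values from separate samples. Mann–Whitney U is a test for two independent samples and has no paired form; the paired counterpart is the Wilcoxon signed-rank test.

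If contingent valuation is used, this is the stated inferential step for objective 5 (section 4.1), and it feeds the preferences document listed as the study's second outcome (section 4.2). A test with the wrong null variance could report no clear preference where there is one, or a preference where there is none.

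**Working it through.** **Inputs from the protocol.** 300 responses from 500 men contacted, at about 60% response; every man values every strategy; tests as quoted. **Not in the protocol.** The within-man correlation rho, the WTP amounts, their SDs and the number of strategies. These are assumed below and rho is shown as a range.

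**The plan's own figure.** 500 × 0.60 = 300, which reproduces. The WTP sample size rests on precedent, with no alpha, power, SD or effect size, so there is no power figure to reproduce.

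**Standard error.** Take n men, two strategies, equal SD and correlation rho.

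- Correct SE of the mean difference: SD × sqrt(2(1−rho)/n)
- SE if the values are treated as independent: SD × sqrt(2/n)
- Ratio, independent to correct: 1/sqrt(1−rho)
- Actual two-sided error of a nominal 5% independent test: 2 × [1 − Phi(1.96/sqrt(1−rho))]

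For power, take n = 300 and a true difference of 0.15 SD. The independent test needs a difference above 1.96 × sqrt(2/300) = 0.160 SD. At rho 0.5 the true SE is sqrt(1/300) = 0.0577 SD. Power is then 1 − Phi((0.160 − 0.150)/0.0577) = 43% for the independent test, and 1 − Phi(1.96 − 0.150/0.0577) = 74% for the paired test.

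| rho (assumed) | SE ratio | Actual error at nominal 5% | Power, independent | Power, paired |
|---|---|---|---|---|
| −0.2 | 0.91 | 7.4% | 46% | 39% |
| 0 | 1.00 | 5.0% | 45% | 45% |
| 0.3 | 1.20 | 1.9% | 44% | 59% |
| 0.5 | 1.41 | 0.56% | 43% | 74% |
| 0.7 | 1.83 | 0.03% | 41% | 92% |

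The higher power of the independent test at rho −0.2 is not a gain, because its error rate there is 7.4% rather than 5%.

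**Does the marginal method fix the sign of rho?** No. Take two strategies. Let b be a man's WTP for his less preferred one, d his increment, and I = 1 if he prefers A (probability p), with b, d and I independent. Then A = b + dI and B = b + d(1−I). Since I(1−I) = 0,

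Cov(A,B) = Var(b) − p(1−p) × mean(d)².

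A large, variable base gives positive correlation. If every man would pay nothing for his less preferred strategy, b = 0 and, with p = 0.5, the covariance is −0.25 × mean(d)², which is negative.

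**Simulations with 300 men.** All amounts are assumed and lognormal. The first row has three strategies, with two compared; the others have two strategies and 20% zero increments. Entries are the percentage of runs rejecting at 5%.

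| Setting | rho | Two-sample t | Mann–Whitney | Paired t | Signed-rank |
|---|---|---|---|---|---|
| Base large relative to increments, real difference | 0.93 | 0 | 0 | 55 | 79 |
| Smaller base, 60:40 preference | 0.07 | 62 | 76 | 64 | 78 |
| Base zero, 50:50 (no difference) | −0.28 | 9 | 12.5 | about 6 | about 6 |

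In the first setting with no true difference, both independent tests rejected in 0% of runs and both paired tests in about 5%. The last row agrees with the formula for the t-test: 1.96/sqrt(1.28) = 1.73, an error of 8.3%.

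**The case against.** **The tests may be meant for groups of men.** The protocol does not say what is compared with what. It later promises to identify whether preferences differ by age, aneurysm size and other factors, and the Work Package 1 survey plans simple group tests followed by regression. Two-sample t and Mann–Whitney tests would suit that purpose. This reading is possible but weaker: the sentence is about preferences for the strategies, and group characteristics are taken up in the next sentence by regression. Even on this reading, it would help to say which comparison each test serves.

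**The t-tests may be paired.** This stands. The word is unqualified, and a reader who infers that both named tests are independent-sample goes beyond the text. Only Mann–Whitney is explicitly so.

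**The values need not be strongly positively correlated.** This also stands. A reader might infer that adding increments to a base forces high positive correlation, and hence that the standard error is always much too large and a clear ranking is hidden. The covariance formula shows that the sign depends on amounts the protocol does not give. Results such as 0% against 79% rejection belong to assumed correlations above 0.9; near rho zero almost nothing is lost.

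**It may never matter.** Contingent valuation is only the fallback, the protocol says the method cannot yet be specified, and an ethics amendment must precede the survey. The tests could also be rerun correctly on the same data. This lowers the priority but does not make Mann–Whitney a suitable test.

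**Conclusion.** The point holds, conditional on contingent valuation being chosen and on the more natural reading that the tests compare strategies. On that reading Mann–Whitney U is the wrong test for the data the protocol describes, and the t-test is left open to the same fault.

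The p-values are then invalid in a direction and by an amount that cannot be fixed from the protocol. For the t-test with equal SDs, over rho from −0.2 to 0.7, the standard error runs from 0.91 to 1.83 times its correct value and the actual error of a nominal 5% test from 7.4% down to 0.03%. Only zero correlation leaves it unharmed. Neither a certain loss of power nor a certain excess of false positives is supported.

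The estimates of mean and median WTP are unaffected. The protocol states no confidence intervals or error bars for WTP, so no planned interval can be called wrong. This should be corrected before the survey if contingent valuation is used; it is not a fault that must stop the study.

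**What to change.** In the Analysis text of the Work Package 2 survey:

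- For differences in WTP between strategies, specify paired t-tests (or a bootstrap that resamples men) for means and Wilcoxon signed-rank tests in place of Mann–Whitney.
- If there are more than two strategies, add a within-man method such as a mixed model with a random effect for man, or a Friedman test.
- Keep two-sample t and Mann–Whitney tests only for comparing groups of men, and say so.

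The cost is a sentence or two. No extra data, men or questionnaire items are needed, and the change can go into the amendment that sections 5 and 8 already foresee for this survey.

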6 STUDY SETTING

The 38 NHS screening providers in England that offer surveillance to men with AAA will be the setting for the study, although only a few of the centres will send names and addresses of men for the surveys.

The University of Sheffield will be the research site. Additionally, there will be 6-8 participant identification centres (PICS) they will all be NHS screening centres in England.

PICS and the NHS sites are appropriate as they help us identify eligible participants quickly and efficiently. The University site is where the research will be coordinated, surveys will be sent from, data will be stored and analysis will take place.

PICS will require Caldicott permission to transfer identifiable data to transfer data to the University.

PICS will identify potential participants only. They will send the list of potential participants to The research team at the University of Sheffield. Only men who have agreed to be contacted for research purposes will be included in this list.

The University will send out surveys and contact people for interviews, focus groups and telephone surveys.

7 SAMPLE AND RECRUITMENT

7.1 Eligibility Criteria

7.1.1 Inclusion criteria

Inclusion criteria for the study are men currently in the AAA surveillance programme, provided by the NHS in England. Only men (people with their gender listed as male on their GP record) are included in the screening and surveillance programme.

Men are invited for their initial screening at 65 so all patient participants will be 65 or over.

All ethnicities and socio-economic groups will be included.

The surveillance programme in England only will be included.

We will endeavour to ensure our 6-8 PICS cover a range of North/South, East/West and urban/rural

Different parts of the study require men in different stages of the programme, this has been described in the work packages above.

For family members of men, the only inclusion criteria is that they are identified by the men as someone who offers them support related to AAA screening. They may be of any gender, age, ethnicity or socio-economic group.

7.1.2 Exclusion criteria

There are no exclusion criteria

7.2 Sampling

7.2.1 Size of sample

Size of samples are described earlier in the methods section of each study component. In addition, we have undertaken a sample size calculation to ensure our survey of men's screening problems is large enough. A 'rule of thumb' approach to sample size for linear regression is $104 + \text{number of predictors}$ for testing coefficients. We have 9 predictors so the sample size could be small: $104 + 9 = 113$. The sample size for testing the whole model would be $50 + (8 \times 9 \text{ predictors}) = 124$. We want to be convinced that some sub-groups have clinically and statistically significantly higher scores (that is, more negative consequences) so we have undertaken a sample size calculation based on a comparison of the mean of a scale in two groups of small vs medium AAAs. With a mean score of 23.74 and a standard deviation of 21.84 on the AAA-related anxiety scale (Aber 2020b), a difference of 5 points (classed as a 'small effect size' of 0.23 and one that our medical co-applicant JM has identified as clinically meaningful) would be identified at the 5% level with 80% power with 300 in each group. That is, we would need 600 respondents in total.

7.2.2 Sampling technique

The sampling technique is described earlier in the methods of each study component. Purposive sampling is used in each qualitative component.

7.3 Recruitment

7.3.1 Sample identification

The sampling technique is described earlier in the methods of each study component.

Each component will recruit differently and should not be taken out of context

No one will be contacted without consent or via public recruitment means.

Men who attend the workshops in work package one will be offered a £30 voucher and travel costs for attending the workshop. No other costs will be paid.

7.3.2 Consent

All potential participants will be assumed to have capacity.

All potential participants will have given consent to be contacted for research purposes.

Consent process are described earlier in the methods of each study component.

8 ETHICAL AND REGULATORY CONSIDERATIONS

Any component of the project that involves men from the screening programme will require NHS ethics and HRA governance approvals.

There are two study components (not described here) that involve health professionals only and we have sought University ethics approval for these components.

Transfer of data from the PIC to the University will require Caldicott approval. This will be applied for once the NHS ethics and HRA approvals have been completed.

Later parts of the project (the feasibility of the new intervention) and the survey on Exit Strategies will require an amendment to be submitted to IRAS as we develop full details of these components.

8.1 Assessment and management of risk

We would like to undertake interviews and workshops in-person, but COVID-19 restrictions may mean that these need to be undertaken virtually or by telephone. We will plan for in-person and then move to virtual if necessary or if preferred by participants.

We will be talking to men about anxiety. We anticipate that some participants may be highly anxious. The Research Associate and Qualitative Researcher have worked with men with AAA before and are used to dealing with this situation sensitively. The Project Manager has not worked with AAA before but is a mental health nurse and has worked with many cases of extreme anxiety linked to physical health conditions. There will also be a specific plan for what to do if a participant gets anxious during the interview. The interview may be stopped (temporarily or permanently), and they may be directed to speak to their GP or AAA nurse. In extreme circumstances they will be given the phone number for the Samaritans. Due to the nature of the questions, we will be asking, it is unlikely that safeguarding issues will arise. However, if they do, we will let the participant know we have a duty to report their situation and we will contact the safeguarding service at their local council. In an immediate life-threatening situation we would call the police.

In the unlikely scenario that a man discloses suicidal thoughts, we will contact the NHS Screening Centre and ask them to notify the man's GP. We will also include in the PIS that men can contact their GP at any time if they feel they are struggling with depression or anxiety.

8.2 Research Ethics Committee (REC) and other Regulatory review & reports

Before the start of the study, a favourable opinion will be sought from a REC for the study protocol, informed consent forms and other relevant documents e.g. advertisements. Parts of the study will require NHS REC and HRA, others will go before our University REC.

For NHS REC reviewed research components

- Substantial amendments that require review by NHS REC will not be implemented until that review is in place and other mechanisms are in place to implement at site.
- All correspondence with the REC will be retained.
- It is the Chief Investigator's responsibility to produce the annual reports as required.
- The Chief Investigator will notify the REC of the end of the study.
- An annual progress report (APR) will be submitted to the REC within 30 days of the anniversary date on which the favourable opinion was given, and annually until the study is declared ended.
- If the study is ended prematurely, the Chief Investigator will notify the REC, including the reasons for the premature termination.
- Within one year after the end of the study, the Chief Investigator will submit a final report with the results, including any publications/abstracts, to the REC.

Regulatory Review & Compliance

Before any site can enrol patients into the study, the Chief Investigator/Principal Investigator or designee will ensure that appropriate approvals from participating organisations are in place.

All participants will be enrolled from the NHS, from 6-8 participant identification centres (PICs). All of the NHS R&D teams will be contacted as close to the start of the IRAS process as possible to apply for NHS REC and HRA approvals to ensure they have capacity and capability to support the study.

Organisational Information Documents will be completed for each site/PIC

Amendments affecting the PICs will be communicated to their R&D teams as soon as possible and the research team will work with the R&D teams to implement the changes once approved by REC/HRA.

End of Study Definition

The end of the study will be the last post-test visit for the intervention feasibility study. We expect that this will be Month 23 (August 2024)

Amendments

NHS REC

Amendments for parts of the study requiring NHS REC/HRA approvals will be undertaken by the senior project manager.

The HRA amendment form will be used to determine if that is substantial or not.

NHS REC /IRAS guidance will be followed for making decisions about amendments to the REC.

University REC

Amendments for parts of the study requiring University REC approval will be undertaken by the senior project manager.

The University has a standard form for applying for an amendment. This standard process will be used and guidance followed.

Amendment history will be recorded in the protocol and, where it affects patients, online.

8.3 Peer review

The study has been externally peer reviewed as part of the NIHR funding application process.

8.4 Patient & Public Involvement

Design of the Research:

There is not an existing AAA surveillance specific PPI group. Therefore, we have established the first one. However, there has been PPI input right from the outset of the research development.

The PPI member on the NAAASP research committee (NMS) was approached to become a co-applicant on the research bid and was involved in the development of the planned research.

During the initial development of the research bid, the views of four men who had also been through the screening process were sought. The men described the impact that screening had had on them, including the anxiety associated with it, and the importance of trying to find ways to reduce this. Two of the original group of four men have also joined the PPI group in order to help take the project forward. The group now consists of six men, who have been through AAA screening or had AAAs that have been surgically repaired. Three members of the group have PPI experience and three do not; training and support has been offered to all.

As the project progresses, we hope to recruit other members to the PPI group who have not been through AAA screening themselves but who may provide support for men that have, such as partners or family members. This will help ensure a wider representation of views within the group.

The PPI group will meet approximately ten times during the study duration. The group will meet at points that are most relevant, and meaningful, to the study so the durations between meetings will be flexible to meet the study needs. For example, at the beginning of the project whilst we are developing study documentation with the input of the PPI group we may need to meet more often.

Patient centred AAA study: PCAAAS

Version 2.1 04.04.23

IRAS 321528

Acceptability of the research:

We are consulting with the PPI group about the most suitable ways of recruiting participants for each work package, to ensure that we can be as inclusive as possible.

We are asking the PPI group to be involved with development of study materials such as invitation letters, consent forms, interview topic guides and survey development to ensure that they are clear and concise.

Management of the Research:

The PPI Lead (LL) and PPI co-applicant (NMS) worked together to develop the agenda for the first PPI meeting that was held two weeks after the project officially commenced. They will continue to do so for further meetings.

Undertaking the Research:

PPI members will attend the two workshops that are planned as part of work package one to help with the co-design of the intervention to reduce screening related anxiety, and to facilitate the inclusion of men and their families/partners in the workshops.

Analysis of the Research:

We do not intend to merely present findings from completed analysis to the group. Rather we would like them to be involved in the analysis in a more meaningful way. This could be through looking at, and discussing, the results of the questionnaires, discussions around coding frameworks for interviews, and through helping with interpretation of findings from the interviews.

Dissemination of Findings:

We would like the group to help establish the best way to disseminate the study findings, including to those that have participated in the research. Some of the PPI group are active on social media and have identified that this may be a way of helping to reach a wide audience as the study progresses. As the group who attend for screening is aged 65 or older we need to ensure that we have a wide range of dissemination approaches.

